### 7.3 Subject Population(s) for Analysis

We expect to enroll 60 patients with various cardiomyopathies including NICM, ICM, and ACM (dilated cardiomyopathy, ischemic cardiomyopathy, and atrial cardiomyopathy). Our goal is to demonstrate improved sensitivity and specificity of identifying viable myocardium and PIR in the ventricles and atria in various cardiac patients to help improve clinical management

## 8 Safety and Adverse Events

### 8.1 Definitions

#### Unanticipated Problems Involving Risk to Subjects or Others

Any incident, experience, or outcome that meets all of the following criteria:

- Unexpected in nature, severity, or frequency (i.e. not described in study-related documents such as the IRB-approved protocol or consent form, the investigators brochure, etc)
- Related or possibly related to participation in the research (i.e. possibly related means there is a reasonable possibility that the incident experience, or outcome may have been caused by the procedures involved in the research)
- Suggests that the research places subjects or others at greater risk of harm (including physical, psychological, economic, or social harm).

#### Adverse Event

An **adverse event** (AE) is any symptom, sign, illness or experience that develops or worsens in severity during the course of the study. Inter-current illnesses or injuries should be regarded as adverse events. Abnormal results of diagnostic procedures are considered to be adverse events if the abnormality:

- results in study withdrawal
- is associated with a serious adverse event
- is associated with clinical signs or symptoms
- leads to additional treatment or to further diagnostic tests

CONFIDENTIAL

This material is the property of Stanford University. Do not disclose or use except as authorized in writing by the study sponsor

- is considered by the investigator to be of clinical significance

### **Serious Adverse Event**

Adverse events are classified as serious or non-serious. A **serious adverse event** is any AE that is:

- fatal
- life-threatening
- requires or prolongs hospital stay
- results in persistent or significant disability or incapacity
- a congenital anomaly or birth defect
- an important medical event

Important medical events are those that may not be immediately life threatening, but are clearly of major clinical significance. They may jeopardize the subject, and may require intervention to prevent one of the other serious outcomes noted above. For example, drug overdose or abuse, a seizure that did not result in in-patient hospitalization, or intensive treatment of bronchospasm in an emergency department would typically be considered serious.

All adverse events that do not meet any of the criteria for serious should be regarded as **non-serious adverse events**.

### **Adverse Event Reporting Period**

The study period during which adverse events must be reported is normally defined as the period from the initiation of any study procedures to the end of the study treatment follow-up. For this study, the study treatment follow-up is defined as 30 days following the last administration of study treatment.

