#### Parameters to be Measured:

A standard physical assessment will be performed on the day of imaging (approximately 1-hour post dosing). Body temperature and respiration rate will be measured within 24 hours prior to dosing and at approximately 1- and 2-hours post dose. A standard 12-lead EKG will be performed both before and after the MR study to assure no significant EKG changes have occurred. Patient's hemodynamics will also be serially monitored. A baseline BP and HR will be performed before beginning the study. After EVP1001-1 contrast infusion, BP and HR will be measured every 2 minutes until 10 minutes post EVP1001-1 contrast infusion after which point a BP and HR will be measured every 5 minutes until the conclusion of the MEMRI and every 10 minutes until the conclusion of DEMRI study. There will be a 5-minute post administration observation interval outside the scanner. The patient will also have continuous EKG monitoring during this time. After the study, the patient will have another standard 12-lead EKG performed to compare with the pre-MRI 12-lead EKG. The patient's symptoms will be

CONFIDENTIAL

This material is the property of Stanford University. Do not disclose or use except as authorized in writing by the study sponsor

reassessed 1 hour after infusion of the EVP1001-1 contrast. A differential and serum chemistry profile (with liver function test) will be performed within a month prior to administration of EVP1001-1 and within 24 hours post EVP1001-1. Adverse events (AEs) and discomforts will be recorded until discharge from the imaging center. At the 24 hour follow-up, the subject will be evaluated by telephone to determine if any AEs occurred from the time the subject left the imaging center. The subjects will have a contact number to report any AEs or to ask questions. Any clinically relevant changes from baseline in vital signs, ECG rhythm, clinical chemistries or physical condition and all AEs will be followed until resolution or until the outcome is known. Injection-associated discomforts will be recorded during administration and until imaging is completed. Primary efficacy will be based on determining whether the heart is normal or abnormal and if abnormal whether there is an infarction, ischemia or both. This provides the basis for calculating sensitivity, specificity, accuracy and predictive values. In addition, the location, size, conspicuity and associated confidence for any disease will be recorded.

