## 8.2 Recording of Adverse Events

At each contact with the subject, the investigator must seek information on adverse events by specific questioning and, as appropriate, by examination. Information on all adverse events should be recorded immediately in the source document, and also in the appropriate adverse event module of the case report form (CRF). All clearly related signs, symptoms, and abnormal diagnostic procedures results should be recorded in the source document, though should be grouped under one diagnosis.

All adverse events occurring during the study period must be recorded. The clinical course of each event should be followed until resolution, stabilization, or until it has been determined that the study treatment or participation is not the cause. Serious adverse events that are still ongoing at the end of the study period must be followed up to determine the final outcome. Any serious adverse event that occurs after the study period and is considered to be possibly related to the study treatment or study participation should be recorded and reported immediately.

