As for intravenous injection of any investigational drug, competent personnel and emergency facilities must be available to address severe and possibly delayed reactions after administration of EVP1001-1 or severe responses to the stress prior to EVP1001-1 administration. Subjects will be observed for AEs starting with the pre-treatment (with ondansetron), during and for at least 1 hour after EVP1001-1 administration during which time emergency equipment will be readily available. AEs will be recorded until discharge from the imaging center. At the 24-hour follow-up, the subject will be evaluated by telephone to determine if any AE occurred from the time the subject left the imaging center. In addition, the subjects will have a contact number to report any AE or to ask questions. Any clinically relevant changes from baseline in vital signs, ECG rhythm, clinical chemistries or physical condition and all AEs will be followed until resolution or until the outcome is known. AEs, if any, will be recorded on the CRF (case report form) along with the action(s) required, time of onset, duration, intensity, and outcome. A judgment will be made by the investigator as to the causality of each event. If a subject has more than one incidence of a given AE, that AE with the greatest severity will be used for analyses. If a cluster of AEs are related, a term describing the syndrome or overall adverse experience should be captured.

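### Adverse events are reportable for 30 days after dosing, but the last dated AE contact is a telephone call at 24 hours, so counts for the defined period are likely to be incomplete

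*Combined protocol and SAP*

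**What the plan says.** **The window.** Section 8.1 (Adverse Event Reporting Period) states that "the study treatment follow-up is defined as 30 days following the last administration of study treatment". Section 8.2 adds: "All adverse events occurring during the study period must be recorded". The AE definition in Section 8.1 counts intercurrent illness and injury, so late events with no evident link to the contrast agent are in scope.

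**The collection schedule.** Section 3.1 (Parameters to be Measured) says: "Adverse events (AEs) and discomforts will be recorded until discharge from the imaging center". It then gives one later contact: "At the 24 hour follow-up, the subject will be evaluated by telephone to determine if any AEs occurred". Section 8.2 repeats both steps: "AEs will be recorded until discharge from the imaging center", then "At the 24-hour follow-up, the subject will be evaluated by telephone to determine if any AE occurred". The post-dose laboratory tests are due "within 24 hours post EVP1001-1", so they bring no later contact either.

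**After the call.** Section 8.2 says that "the subjects will have a contact number to report any AE or to ask questions". It also tells the investigator to ask about AEs at every contact. The secondary objective in Section 2 describes Aim 2 as a clinical follow-up for cardiovascular events, without time, method or duration. Section 8.1 mentions a last scheduled visit (Post-study Adverse Event) but does not date it.

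**The concern.** The plan sets a 30-day obligation and a schedule for meeting it that ends on day 1. From then on, an event enters the data only if the patient calls or some undated contact happens to pick it up.

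Safety and tolerance, judged partly on AEs, are among the key endpoints in Section 3.2. Other rules also depend on the site learning of late events. The stopping rules in Sections 3.1 and 8.3.1 name cardiovascular death, myocardial infarction, hospitalization and syncope. Section 8.3.1 requires serious AEs to reach the sponsor within 24 hours, and all deaths to reach the IRB within 72 hours at most. A patient who is incapacitated or has died cannot use the contact number. A report that described safety over the defined period would rest mostly on days when no one was scheduled to ask.

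**Working it through.** The plan gives no expected AE rate and no AE incidence calculation, so there is no figure of its own to reproduce. The check compares the stated rules and then shows how far the result depends on assumptions.

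**1. Days without a dated contact**
- Reporting period: 30 days (Section 8.1).
- Last dated AE contact: 24 hours, that is day 1 (Sections 3.1 and 8.2).
- 30 − 1 = 29 days.

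This counts days. It does not estimate the share of events lost.

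**2. Do other provisions fill the 29 days?**

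| Provision | Does it cover days 2 to 30? |
|---|---|
| Contact number (3.1, 8.2) | Yes, for any AE, but only if the patient calls |
| Questioning at each contact (8.2) | Only if a contact takes place; none is dated |
| Aim 2 follow-up (2) | Possibly; undated, and aimed at cardiovascular events |
| Last scheduled visit (8.1) | Possibly; undated |
| Following AEs to resolution (3.1, 8.2) | Only for events already known |
| Procedures flowchart (listed in 14) | Cannot be checked; not in the text reviewed |

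**3. Direction and size for all AEs**

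Let L be the share of AEs that begin after the 24-hour call, and c the share of those that are reported anyway. Then

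observed / true = 1 − L(1 − c).

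Sections 1.1 and 1.4 say that more than 93% of Phase I AEs arose no later than a minute from dosing. That leaves under 7% for all later times, so L would be at most 7% if the pattern carries over. The larger values of L, and all values of c, are assumptions.

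| L | c = 0 | c = 0.5 | c = 1 |
|---|---|---|---|
| 7% | 0.93 | 0.965 | 1.00 |
| 20% | 0.80 | 0.90 | 1.00 |
| 50% | 0.50 | 0.75 | 1.00 |

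The ratio never exceeds 1, so any bias is downward.

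**4. Late events alone**

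Let q be a patient's risk of a late event (assumed) and c = 0.5 (assumed). N = 50 comes from the Study Summary and Section 2; other sections give 60 or 120.
- Expected events = Nq.
- P(none reported) = (1 − qc)^N.
- P(at least one missed) = 1 − (1 − q(1 − c))^N.

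| q | Expected | Expected reported | P(none reported) | P(at least one missed) |
|---|---|---|---|---|
| 2% | 1.0 | 0.5 | 61% | 40% |
| 5% | 2.5 | 1.25 | 28% | 72% |
| 10% | 5.0 | 2.5 | 8% | 92% |

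With full reporting at q = 5%, the chance of seeing no late event would be 0.95^50 = 8%, against 28% here. These rows illustrate the mechanism and do not predict this trial's results.

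**The case against.** The strongest reply is that the schedule suits the product. EVP1001-1 is given once, its primary blood half-life is under 1 minute (Section 1.1), and AEs in heart patients to date arose at dosing (Section 1.5). Active questioning to 24 hours with spontaneous reporting afterwards is a defensible design. On this view the 30 days says when an AE must be reported, not how long patients are questioned.

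Much of this stands. It supports 24 hours as a possible choice, but that is not the choice Section 8.1 writes down, and Section 8.2 asks for all AEs in the period. The Phase I timing is also limited evidence: the observation window is not given, and that study had no serious AEs. It says little about late events in patients with cardiomyopathy.

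Three stronger readings are tempting, and the documents do not support them.
- A reader might infer that a 30-day AE rate will be reported and will be too low. No such rate is a planned endpoint; Section 3.2 speaks of the type and extent of AEs, and Section 7 plans no AE incidence.
- A reader might infer that events the patient thinks unrelated are filtered out. The contact number accepts any AE. The relatedness condition in Section 8.1 applies to events after the last scheduled visit, and it includes the view of the patient's own physician.
- A reader might infer that nothing but patient calls can reveal a late event. The Aim 2 follow-up, with questioning at each contact, or the flowchart could add a contact within 30 days. Neither can be shown to do so.

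**Conclusion.** The point holds as a conflict between two stated rules: a 30-day period in which all AEs must be recorded, and dated collection that ends at 24 hours, leaving 29 days without a dated contact. AE and serious AE counts for the defined period are likely to be incomplete, and the error can only be downward.

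The size cannot be fixed from the documents. If the Phase I timing carries over, under 7% of all AEs are exposed to loss. That small share would consist of the late intercurrent and serious events that a 30-day window exists to catch. The conclusion assumes that the missing flowchart adds no dated contact after 24 hours and that the Aim 2 follow-up does not reliably fall within 30 days. If either does, the gap narrows or closes and the text only needs to say so. The change should be made, but the matter does not by itself invalidate the trial.

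**What to change.** First check the procedures flowchart for a contact after 24 hours. Then reconcile the AE text in Sections 3.1, 8.1 and 8.2 in one of two ways.

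1. **Keep 30 days.** Add one scripted telephone contact at day 30 covering vital status, hospitalizations, and new or worsened symptoms. Make it for every dosed patient who has not withdrawn consent to contact, including those who did not complete imaging. A dated Aim 2 contact could serve the same purpose. Amend the discharge wording in Sections 3.1 and 8.2 to match.
2. **Shorten the active period.** State that active ascertainment ends at 24 hours and that later events come from spontaneous reports only. Limit any safety claim to match.

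In either case, give the Aim 2 follow-up a stated time and method.

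The first option costs one short call per patient and a line on the CRF. It will also bring some background-disease events into the AE counts of a study with no control group; the onset time and causality judgment that Section 8.2 already collects help to set these apart. The second option costs almost nothing, but it gives up any claim about days 2 to 30 beyond what patients volunteer.

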### **Pre-existing Condition**

A preexisting condition is one that is present at the start of the study. A preexisting condition should be recorded as an adverse event if the frequency, intensity, or the character of the condition worsens during the study period.

### **General Physical Examination Findings**

At screening, any clinically significant abnormality should be recorded as a preexisting condition. At the end of the study, any new clinically significant findings/abnormalities that meet the definition of an adverse event must also be recorded and documented as an adverse event.

### **Post-study Adverse Event**

All unresolved adverse events should be followed by the investigator until the events are resolved, the subject is lost to follow-up, or the adverse event is otherwise explained. At the last scheduled visit, the investigator should instruct each subject to report any subsequent event(s) that the subject, or the subject's personal physician, believes might reasonably be related to participation in this study. The investigator should notify the study sponsor of any death or adverse event occurring at any time after a subject has discontinued or terminated study participation that may reasonably be related to this study. The sponsor should also be notified if the investigator should become aware of the development of cancer or of a congenital anomaly in a subsequently conceived offspring of a subject that has participated in this study.

### **Abnormal Laboratory Values**

A clinical laboratory abnormality should be documented as an adverse event if any one of the following conditions is met:

- The laboratory abnormality is not otherwise refuted by a repeat test to confirm the abnormality
- The abnormality suggests a disease and/or organ toxicity
- The abnormality is of a degree that requires active management; e.g. change of dose, discontinuation of the drug, more frequent follow-up assessments, further diagnostic investigation, etc.

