
over time, offering potential benefits over the nonspecific extracellular agents currently available for MRI or X-ray/CT procedures. This feature allows full use of the high resolution of MRI, since there is not a trade-off of high spatial resolution for temporal (first-pass) resolution. It is anticipated that the features offered by EVP1001-1 along with the high resolution, three-dimensional attributes of MRI will result in higher accuracy than is available with other current modalities in practice, including stress echocardiograms, cardiac MRI using gadolinium contrast and nuclear studies such as SPECT and PET. This will be evaluated in this study and serve as the basis for pivotal registration studies. All components of EVP1001-1 are USP and are approved for use as drugs in man, orally and/or intravenously. A summary of the Phase I safety and PK (pharmacokinetics) study are provided below. The Phase I study evaluated the safety and tolerance of EVP1001-1 in humans, with special emphasis on cardiovascular safety, and assessed its PK profile. Overall, EVP1001-1 was found to be safe at all doses. There were no serious adverse events (SAE) or any events requiring medical treatment. Of special importance, no signs of cardiac depression were reported. In addition, there was no observation of prolongation of the QTc or PR intervals or other ECG-changes that had previously been reported in animals for Mn. There were no changes in hematology, serum biochemistry (including liver function tests), coagulation parameters nor in temperature, respiratory rate or blood oxygen levels. Transient increases in HR and BP were seen. These, for the most part, reflected transient changes within the normal reference range. There was no obvious dose-relationship for these responses, although their duration and magnitude were greater for the 5-minute than for the 1-minute dose administrations. Other AEs were reported, almost all which were regarded as of mild or moderate intensity. Almost all events occurred during or immediately after dosing and resolved within minutes. Over 83% of the AEs occurred during dosing and over 93% occurred within one minute of dosing. Nearly one-third of all events resolved within one minute from dosing, over 80% within 5 minutes, and 94% resolved within 1 hour. The most frequent types of AEs were injection-associated discomforts (warmth, flushing, cold, pressure, injection site changes, increased HR/BP), gastrointestinal disturbances (discomforts, nausea, vomiting, diarrhea), lacrimation and headache. Although gastrointestinal disturbances, such as nausea and occasional vomiting, resolved rapidly without treatment, these bothersome events may be avoidable through the use of a standard anti-emetic. This proved to be beneficial in humans and also in high-dose animal studies. The PK profile reflected that known for Mn in humans (based on reported radiotracer Mn studies), with a primary blood half-life under 1 minute, and less than 1% of the dose remained in the blood by 30 minutes after dosing. The performance of EVP1001-1 was as expected based on information that was in the Investigators' Brochure. Lastly, please refer to US Patent #5,980,863 regarding further details of EVP1001-1 contrast ingredients.

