### **4.2 Exclusion Criteria**

- have a positive pregnancy test (females)
- received an investigational drug or device within 30 days prior to administration of EVP1001-1

- have known hypersensitivity to ondansetron or other selective serotonin 5HT3 receptor blockers
- are taking a digitalis preparation or calcium channel blocker within 30 days to MRI
- Contraindication to receiving metoprolol
- have a history of torsades or prolonged QT/QTc interval (QTc > 470 msec)
- have NYHA Grade IV heart failure or EF less than 25
- have abnormal liver function tests or a history of liver disease (2 times upper limits of normal)
- have stage 11 hypertension (Systolic Blood Pressure > 140 or Diastolic BP > 90 consistently at baseline)
- have abnormal baseline potassium or calcium (outside normal reference ranges)
- hemoglobin less than 10 g/dl
- Have a history of ventricular arrhythmia per stress test or monitoring
- No recent cardiac intervention within 90 days (CABG, Valve, PTCA)
- No recent CHF, MI or Angina within 60 days
- Conduction disease (QRSd >120 msec or Sick Sinus Syndrome.)
- No cardiac implantable device
- Weight not to exceed 300 kgs and/or chest circumference .36cms
- 

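### Section 8.1 gives two incompatible rules for when an abnormal laboratory value is an adverse event, and the looser one admits reference-range noise into the safety endpoint

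*Combined protocol and SAP*

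**What the plan says.** Two parts of section 8.1 govern abnormal laboratory results.

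- **Abnormal Laboratory Values:** "A clinical laboratory abnormality should be documented as an adverse event if any one of the following conditions is met". The first condition reads "The laboratory abnormality is not otherwise refuted by a repeat test to confirm the abnormality". The other two are that the value points to disease or organ toxicity, or that it needs active management.
- **Adverse Event:** the general definition is "any symptom, sign, illness or experience that develops or worsens in severity during the course of the study". A narrower rule for test results follows: "Abnormal results of diagnostic procedures are considered to be adverse events if the abnormality" meets one of five conditions. These are that it ends the patient's participation, goes with a serious AE, goes with signs or symptoms, prompts extra treatment or tests, or "is considered by the investigator to be of clinical significance".

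Section 3.1 (Parameters to be Measured) schedules a differential and a chemistry panel with liver tests once within the month before dosing and once within 24 hours after it. It schedules no repeat and does not give the number of analytes.

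Section 3.2 bases safety and tolerance on AEs, injection-associated discomforts, and changes in laboratory values, vital signs and ECG. It also plans a pre/post comparison of laboratory parameters.

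On discomforts, section 3.1 adds: "Injection-associated discomforts will be recorded during administration and until imaging is completed". An earlier sentence in that section has AEs and discomforts recorded up to discharge. In the Phase I summary (sections 1.1 and 1.4) discomforts were counted as AEs: "The most frequent types of AEs were injection-associated discomforts".

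**The concern.** A laboratory result slightly outside its range, with no symptoms, no action taken and no repeat, is an AE under Abnormal Laboratory Values and is not one under Adverse Event. The protocol does not say which rule prevails. Two people coding the same CRF could both follow the protocol and report different AE rates.

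Safety and tolerance are among the key endpoints in section 3.2, and section 7.2 gives no separate safety analysis. The AE definitions therefore largely decide what the safety result will look like. If the looser rule is applied as written, part of the reported AE incidence will reflect how many analytes are on the panel, not the contrast agent.

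A second, smaller gap concerns discomforts. Sections 3.1 and 3.2 name them beside AEs without saying whether a discomfort is also coded as an AE. Section 8.2 asks for intensity, duration, causality and outcome for AEs only. A discomfort logged under its own label might lack those fields, and one logged under both labels might be counted twice. Either would blur the comparison with Phase I.

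**Working it through.** **Step 1: the two laboratory rules compared**

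| Post-dose result | Abnormal Laboratory Values | Adverse Event |
|---|---|---|
| Trivial, no symptoms, not repeated | AE (not refuted) | Not an AE |
| Trivial, no symptoms, repeat normal | Not an AE by the first condition | Not an AE, unless the repeat counts as a further test |
| Judged clinically significant, not repeated | AE | AE |

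The first row is the contradiction. The list also defeats itself. If it is enough that a value was not refuted, the second and third conditions can add only values that a repeat has already refuted. They do useful work only if the first condition is a precondition, which suggests a drafting slip.

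**Step 2: possible size**

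The plan states no AE rate, so there is no figure to reproduce. What follows is an illustration.

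Assumptions, none of them from the documents: k = 10, 20 or 25 analytes; each reference range covers 95% of unaffected values; analytes are independent; the drug has no effect; each analyte's baseline and post-dose values are bivariate normal with within-person correlation ρ.

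*Any out-of-range value at the post-dose draw:* P = 1 − 0.95^k, which is 40% for k = 10, 64% for k = 20 and 72% for k = 25.

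This includes values already abnormal at baseline. The fairer count takes only new abnormalities, in range before and out of range after:

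- Per analyte, p = 0.95 − P(both in range).
- For ρ = 0, p = 0.95 − 0.95² = 0.0475.
- For ρ = 0.9, the bivariate normal gives p = 0.0204.
- Per patient, P(at least one) = 1 − (1 − p)^k.

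| k | ρ = 0 | ρ = 0.5 | ρ = 0.8 | ρ = 0.9 |
|---|---|---|---|---|
| 10 | 38.5% | 34.0% | 24.8% | 18.6% |
| 20 | 62.2% | 56.5% | 43.4% | 33.7% |
| 25 | 70.4% | 64.7% | 50.9% | 40.2% |

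The extremes are 1 − (1 − 0.0204)^10 = 18.6% and 1 − (1 − 0.0475)^25 = 70.4%. For the 50 patients of the Study Summary and section 2 (other sections give 60 or 120), that is 50 × 0.186 ≈ 9 to 50 × 0.704 ≈ 35 patients.

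The expected number of such values per patient is k × p, from 10 × 0.0204 = 0.20 to 25 × 0.0475 = 1.19. This number does not need independence between analytes. The percentages do, and positive correlation between analytes would lower them.

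**Step 3: discomforts**

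A new discomfort is a symptom that develops during the study, so it fits the general AE definition, and Phase I classified it that way. No section says it is not an AE, and none says it is to be entered as one. The share that might be coded differently cannot be computed from the documents.

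**The case against.** The strongest reply is that no stated decision depends on the AE count. The study is open-label and single-arm, with no AE-rate hypothesis or threshold. The stopping provisions in sections 3.1, 8.3.1 and 8.4 rest on cardiovascular or serious events. The first laboratory condition mentions a repeat test, so staff may well do one, and section 3.1 follows clinically relevant changes to resolution. This stands as a limit on the consequences. It does not remove the contradiction, because no repeat is required and section 3.2 still reports AEs as part of a key endpoint.

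Four stronger readings are tempting, and the documents do not support them.

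- *Unchanged baseline abnormalities would become AEs.* A reader might infer this from the exclusion "have abnormal liver function tests or a history of liver disease (2 times upper limits of normal", which seems to admit mildly raised liver tests. But the general definition requires onset or worsening, and the Pre-existing Condition paragraph also requires worsening. Section 4.3 lists abnormal liver tests and abnormal calcium, potassium or hemoglobin as exclusions and carries these over to the new patients.
- *The commonest reactions would be lost.* Discomforts are recorded, fit the AE definition and are named in the section 3.2 endpoint. The fault is unclear labelling.
- *A primary AE count is distorted.* No such count is defined. Nor do the laboratory and discomfort provisions contradict each other: they cover different things.
- *Phase I bounds the share of AEs that might be relabelled at 83%.* The figure given is over 83% of AEs during dosing. That is a floor, and it describes timing, not type.

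It also cannot be said that the stricter rule would yield almost no laboratory AEs, since it counts any abnormality that leads to further tests or treatment.

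**Conclusion.** The contradiction between the two parts of section 8.1 is real and stands in the current text. Applied literally and without repeats, the looser rule could give about 19% to 70% of patients (roughly 9 to 35 of 50) at least one laboratory AE from reference-range variation alone. That range rests on the assumed analyte number, independence, 95% ranges and within-person correlation. Routine repeats or correlated analytes would bring it down. It shows that the wording matters and is not a forecast.

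The discomfort point is a secondary clarification: a missing coding rule, with a risk of omission or double counting that cannot be sized. Both points affect how the safety result is described and compared with Phase I. Neither affects a test or a stopping decision. They are worth settling before AEs are coded.

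**What to change.** 1. In Abnormal Laboratory Values, make the repeat-test condition a precondition: the abnormality has not been refuted **and** at least one other condition holds. Align those other conditions with the list under Adverse Event, so that section 8.1 contains one rule.
2. Require onset or worsening relative to the patient's own baseline panel.
3. State whether a confirmatory repeat is expected, and that ordering one does not by itself count as a further diagnostic test.
4. Report all other laboratory shifts in the pre/post comparison that section 3.2 already plans, not as AEs.
5. In sections 3.1 and 3.2, state that injection-associated discomforts are coded as AEs with an injection-associated flag and carry the same intensity, duration, causality and outcome fields as other AEs. Give them one recording end point. Tabulate AE incidence with and without the flag.

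The cost is protocol wording and some CRF fields. The downside is a higher reported rate of mild AEs once discomforts are coded as AEs. The flagged tabulation makes that visible and keeps the results comparable with Phase I.
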